4.2 Exclusion criteria

As in the core study CQGE031C2201, patients fulfilling any of the following criteria are not eligible for inclusion in this study.

No additional exclusions may be applied by the investigator, in order to ensure that the study population will be representative of all eligible patients.

1. Use of other investigational drugs at the time of enrollment into the extension study or within 30 days or 5-half-lives prior to visit 206, whichever is longer
2. Patients with a stool examination positive for ova and parasites (stool sample taken at visit 206).
3. New onset or signs and symptoms of any form of chronic urticaria other than CSU during the follow-up epoch of study CQGE031C2201. This includes the following:
 - Inducible urticaria: urticaria factitia, cold, heat, solar, pressure, delayed pressure, aquagenic, cholinergic, or contact urticarial per investigator's evaluation
 - Diseases with possible symptoms of urticaria or angioedema such as urticarial vasculitis, erythema multiforme, cutaneous mastocytosis (urticaria pigmentosa), and hereditary or acquired angioedema (e.g., due to C1 inhibitor deficiency)
4. Any other skin disease associated with chronic itching that might confound the study evaluations and results (e.g. atopic dermatitis, bullous pemphigoid, dermatitis herpetiformis, senile pruritus etc.)
5. Onset or ongoing alcohol or drug abuse, within the last 6 months
6. Unable to comply with study and follow-up procedures during the entire treatment and follow-up period
7. Use of prohibited treatment as detailed in protocol ([Table 5-1](#))
8. Hypersensitivity to any of the study drugs i.e. QGE031, fexofenadine, loratidine, cetirizine, or epinephrine or any of the ingredients or its components, or to drugs of similar chemical classes (i.e. to murine, chimeric, or human antibodies)
9. History of anaphylactic shock

10. Onset of malignancy of any organ system within the past 1 year (except for basal cell carcinoma or actinic keratoses or Bowen disease (carcinoma in situ) that have been treated with no evidence of recurrence in the past 12 weeks; carcinoma in situ of the cervix or non-invasive malignant colon polyps that have been removed)
11. Onset of clinically significant cardiovascular (such as but not limited to myocardial infarction, unstable ischemic heart disease, NYHA Class III/IV left ventricular failure arrhythmia, uncontrolled hypertension within 12 months prior to visit 206), neurological, psychiatric, metabolic, or other pathological conditions such as but not limited to cerebrovascular disease, neurodegenerative diseases, or other neurological disease, uncontrolled hypo- and hyperthyroidism and other autoimmune diseases, hypokalemia, hyperadrenergic state, or ophthalmologic disorder that could interfere with the compromise the safety of the patients, interfere with evaluation or interpretation of the study results, or preclude completion of the study
12. Medical examination or laboratory findings that suggest the possibility of decompensation of co-existing conditions for the duration of this study. Any items that are cause for uncertainty will be reviewed with the investigator
13. History or current treatment for hepatic disease including but not limited to acute or chronic hepatitis, cirrhosis or hepatic failure or AST/ALT levels or INR of more than 1.5x upper limit of normal (ULN)
14. History of renal disease or creatinine level above 1.5x ULN at visit 206
15. Platelets < 100,000/ μ L at visit 206
16. Long QT syndrome or whose QTcF (Fridericia) measured at end of core study visit (Visit 206) is prolonged (> 450 ms for males or > 460 ms for females) and confirmed by a central assessor (ECG measurement should not be repeated in these patients to confirm eligibility)
17. Pregnant or nursing (lactating) women, where pregnancy is defined as the state of a female after conception and until the termination of gestation, confirmed by a positive hCG laboratory test
18. Women of child-bearing potential, defined as all women physiologically capable of becoming pregnant, unless they are using effective methods of contraception during dosing of study treatment. Effective contraception methods include:
 - Total abstinence (when this is in line with the preferred and usual lifestyle of the subject. Periodic abstinence (e.g., calendar, ovulation, symptothermal, post-ovulation methods) and withdrawal are not acceptable methods of contraception
 - Female sterilization (have had surgical bilateral oophorectomy with or without hysterectomy) or tubal ligation at least six weeks before taking study treatment. In case of oophorectomy alone, only when the reproductive status of the woman has been confirmed by follow up hormone level assessment
 - Male sterilization (at least 6 m prior to screening in core study). For female subjects on the study, the vasectomized male partner should be the sole partner for that subject
 - Barrier methods of contraception:
 - Male or female condom with or without spermicide
 - Cap, diaphragm, or sponge with spermicide

- Use of oral, injected or implanted hormonal methods of contraception or other forms of hormonal contraception that have comparable efficacy (failure rate <1%), for example hormone vaginal ring or transdermal hormone contraception
- Placement of an intrauterine device (IUD) or intrauterine system (IUS)
In case of use of oral contraception women should have been stable on the same pill for a minimum of 3 months before taking study treatment.

Note: Women are considered post-menopausal and not of child bearing potential if they have had 12 months of natural (spontaneous) amenorrhea with an appropriate clinical profile (e.g., age appropriate, history of vasomotor symptoms) or have had surgical bilateral oophorectomy (with or without hysterectomy) or tubal ligation at least 6 weeks ago. In the case of oophorectomy alone, only when the reproductive status of the woman has been confirmed by follow-up hormone level assessment is she considered not of child bearing potential.

5 Treatment

5.1 Protocol requested treatment

5.1.1 Study treatment

The following will be prepared by Novartis and supplied to the Investigative site as open-label medication of liquid formulation vials:

- QGE031 120mg/mL solution for subcutaneous injection is provided in 2mL glass vials each containing 1mL QGE031 solution at 120mg/mL. [REDACTED]

[REDACTED] The solution is clear to opalescent, colorless to yellowish in 2mL glass vials with rubber stopper and aluminum flip-off cap and is ready-to-use for subcutaneous injection.

5.1.2 Additional study treatment

No additional treatment beyond study treatment is requested for this trial.

Patients will continue to use their background medication i.e H1-AH at approved or increased doses alone or in combination with H2-AH and/or a LTRA (standard of care) with a stable regimen during the study.

[figure not shown]
5.2 Treatment arms

Patients will all be treated with QGE031 240 mg sc q 4 weeks for 52 weeks (13 treatments) in this open label study.

5.3 Treatment assignment, randomization

This is a single-arm study and all patients will receive QGE031 treatment.

At Visit 301, all eligible patients will be enrolled via Interactive Response Technology (IRT). The investigator or his/her delegate will contact the IRT system after confirming that the patient fulfills all the inclusion/exclusion criteria. The IRT will assign a unique medication

number for the first package of study treatment (QGE031) to be dispensed to the patient. There will be no randomization.

5.4 Treatment blinding

In this extension study, treatment is open-label; patients, investigator staff, persons performing the assessments, the sponsor and data analysts will know that all patients receive QGE031 q4w.

Randomization/treatment assignment data from the study CQGE031C2201 will be kept strictly confidential and will not be unblinded to the extension study sites at least until the core study CQGE031C2201 is fully completed. The site staff including the unblinded pharmacist who prepared the study treatment in the core study CQGE031C2201 must ensure that blinding for the core study is strictly maintained. To avoid any biased assessments in the extension study, the unblinded pharmacist or designee from the core study cannot be involved in the extension study other than to prepare and/or administer the open-label QGE031 in the extension study.

5.5 Treating the patient

5.5.1 Patient numbering

Each patient was uniquely identified by a Subject Number in the core study CQGE031C2201, which is composed by the site number assigned by Novartis and a sequential number assigned by the investigator. In this extension study, the subject numbers will remain the same as assigned during the core study CQGE031C2201; no new subject numbers will be assigned.

The same RDC database will be used for both the core and the extension study. Study visits related to the extension study will become available once the patient has completed the core study and the site has indicated in the eCRFs that the patient will continue into the extension study.

[figure not shown]
Upon signing the informed consent for the extension study, the investigator or his/her staff will contact the IRT and provide the requested identifying information for the patient to register them into the IRT system.

If the patient fails to be treated for any reason, the IRT must be notified within 2 days that the patient was not treated. The reason for not being treated will be entered on the Treatment Epoch Disposition form.

5.5.2 Dispensing the investigational treatment

Each study site will be supplied by Novartis with investigational treatment in packaging of identical appearance.

All patients will receive QGE031 240mg (2 vials) at each study drug administration and supplies will be provided in 2 boxes (1 vial in one box). Each vial is 120mg/1ml. The investigational treatment packaging has a 2-part label. A unique medication number is printed on each part of this label. Investigator staff will identify the investigational treatment package(s) to dispense to the patient by contacting the IRT and obtaining the medication

number. Immediately before dispensing the medication to the patient, investigator staff will detach the outer part of the label from the packaging and affix it to the source document (Drug Label Form) for that patient's unique subject number.

5.5.3 Handling of study treatment

5.5.3.1 Handling of investigational treatment

Investigational treatment must be received by a designated person at the study site, handled and stored safely and properly, and kept in a secured location to which only the investigator and designees have access. Upon receipt, all investigational treatment should be stored according to the instructions specified on the labels. Clinical supplies are to be dispensed only in accordance with the protocol. Technical complaints are to be reported to the respective Novartis CPO Quality Assurance.

Medication labels will be in the local language and comply with the legal requirements of each country. They will include storage conditions for the investigational treatment but no information about the patient except for the medication number.

The investigator must maintain an accurate record of the shipment and dispensing of investigational treatment in a drug accountability log. Monitoring of drug accountability will be performed by the field monitor during site visits or remotely and at the completion of the trial. Patients will be asked to return all unused investigational treatment and packaging throughout, at the end of the study or at the time of discontinuation of investigational treatment.

At the conclusion of the study, and as appropriate during the course of the study, the investigator will return all unused investigational treatment, packaging, drug labels, and a copy of the completed drug accountability log to the Novartis monitor or to the Novartis address provided in the investigator folder at each site.

5.5.3.2 Handling of other study treatment

Not applicable.

5.5.4 Instructions for prescribing and taking study treatment

All study drug administrations can be done in an outpatient ambulatory clinic setting. Study drug will be administered by a pharmacist or designee. Blinded personnel involved in core study can prepare and administer drug in this extension study. Subjects will remain on-site for observation for a period of 2 hours for the first 3 study drug administrations (Visit 301, 302 and 303) and 30 minutes for subsequent drug administration visits (304 to 313). This observation period follows the recommendation suggested by the National Heart, Lung, and Blood Institute and by The American Academy of Allergy, Asthma & Immunology and the American College of Allergy, Asthma and Immunology Executive Committees Joint Task Force (Cox et al 2007) for the anti IgE therapy currently available (omalizumab).

Two injections are required to administer the dose of 240 mg. The injections can be administered in the deltoid region on the right and/or left arm, and/or on the right and/or left thigh, or the abdomen as preferred by patient and/or site. The injections are administered

subcutaneously after aspiration of the plunger of the syringe. If blood appears at the hub or blood is withdrawn into a syringe, the needle is removed without administration of the dose and the injection site is changed. Each injection must be administered at a different site (e.g., right arm and left thigh).

The guidelines for the preparation and administration of study medication are described in the pharmacist manual.

All dosages prescribed and dispensed to the patient and all dose changes during the study must be recorded on the Dosage Administration Record CRF.

5.5.5 Permitted dose adjustments and interruptions of study treatment

Study drug dose adjustments are not permitted. Study drug interruption is only permitted if the investigator considers an interruption necessary for the treatment of an adverse event. An interruption of two (2) consecutive study drug administrations or three or more administrations in total should be discussed with Novartis or delegate regarding the patient's eligibility to continue investigational treatment.

Any missed or altered study drug administrations must be recorded on the Dosage Administration Record CRF in order to reconstruct an accurate dosing history for each patient.

5.5.6 Rescue medication

Fexofenadine, loratadine, and cetirizine (H1-AH), in addition to being used as background medication will be allowed as rescue medication and used on an as needed basis during treatment and follow-up epochs. The selection of any one rescue medication should be made once for an individual patient. A switch of the rescue medication for an individual patient or between the core and extension study is not permitted. The patients will use the rescue medication at the indicated dose. If required for symptomatic relief, patients may take up to 4x the approved dose of the rescue medication, depending on local clinical practice and guideline. H1-AH rescue medication will be sourced locally.

As an additional safety precaution for the treatment of anaphylactic reactions, patients will be supplied with epinephrine, either via an auto-injector (if available) or as per other local standard of care. The investigator will train the patients on how to detect such reactions and how to use epinephrine. After any use of epinephrine, patients will need to seek immediate medical attention to ensure that the initial reaction has been successfully controlled and/or to trigger additional therapeutic steps.

The use of epinephrine will be recorded on the concomitant medication CRF page.

5.5.7 Concomitant treatment

This study requires concurrent use of H1-AH alone (at approved doses as per local health authority guidance or at increased doses up to four-fold) or in combination with H2-AH and/or LTRA (montelukast, zafirlukast, pranlukast) as background medication.

It is recommended that patients should remain on a stable treatment regimen (H1-AH alone or in combination with H2-AH and/or LTRA) throughout the study.

The investigator should instruct the patient to notify the study site about any new medications he/she takes after the patient was enrolled into the study. All medications, procedures and significant non-drug therapies (including physical therapy and blood transfusions) administered after the patient was enrolled into the study must be recorded on the respective CRF pages.

5.5.8 Prohibited Treatment

[figure not shown]
Consistent with the core study CQGE031C2201, the use of the treatments displayed in [Table 5-1](#) is NOT allowed after the start of study treatment. The minimum required period without prohibited treatment before Visit 206 is listed in [Table 5-1](#) as well. Each concomitant drug must be individually assessed against all exclusion criteria and the table below to see if it is allowed. If in doubt, the investigator should contact Novartis or delegate before randomizing a patient or allowing a new medication to be started. If the prohibited treatment was used during the study for any indication, the patient must discontinue use of the prohibited treatment if he/she wishes to continue in the study. If the patient received a live virus vaccination during the study, the patient must discontinue study treatment

Table 5-1 Prohibited Treatment

Medication	Minimum required period without medication before Visit 301
Beta-blocker therapy	7 days
Routine (daily or every other day during 5 or more consecutive days) doses of systemic corticosteroids	30 days
Routine (daily or every other day during 5 or more consecutive days) doses of hydrochloroquine	30 days
Routine (daily or every other day during 5 or more consecutive days) doses of methotrexate, cyclosporine A, cyclophosphamide, tacrolimus and mycophenolate mofetil)	30 days
Intravenous immunoglobulin G	30 days
Plasmapheresis	30 days
Regular (daily or every other day) doxepin (oral)	14 days
Inactive vaccination	48 hours prior to any visit
Live attenuated vaccine	30 days

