- No study treatment will be given during the post-treatment follow-up epoch; however, patients are allowed to take background medication and rescue medication. If a subject relapses i.e. develops symptoms with an UAS7 ≥ 12 , the investigator should be contacted for an ad-hoc visit to consider treatment with standard of care or other therapy.

Figure 3-1 Study design

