5.6 Study completion and discontinuation

5.6.1 Study completion and post study treatment

Study completion for individual patients will be when he/she has completed the extension study 52 weeks of treatment and the full follow-up epoch up to and including Visit 405.

Treatment completion will be when the patient completed the full 52-week treatment epoch. If patients relapse during the follow-up epoch of the extension study as defined by a UAS7 \geq 12, they will be allowed to exit the study if desired and receive conventional therapy at the discretion of the investigator.

Completion of the study will be considered when all patients will have completed 52 weeks of treatment epoch and the full follow up epoch or have prematurely withdrawn from the study.

Information on the subject's completion or discontinuation of the study and the reason for discontinuation of the study will be recorded on the appropriate Study Epoch Completion eCRF page.

When the patient has completed all scheduled study assessments, the investigator must call or logon to the IRT system to record the patient completion as per above completion definitions.

The following is recommended for initiating other treatment outside or post study:

- A wash-out of QGE031 of at least 4 months is advised prior to commencing Xolair® treatment

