5.6.2 Discontinuation of study treatment

Patients may voluntarily discontinue study treatment for any reason at any time.

The investigator should discontinue study treatment for a given patient if, on balance, he/she believes that continuation would be detrimental to the patient's well-being.

As in study CQGE031C2201E1, study treatment must be discontinued under the following circumstances:

- Adverse events for which continued exposure to the study drug would be detrimental
- Abnormal renal laboratory results requiring discontinuation (see [Section 7.4](#))
- Abnormal liver laboratory results requiring discontinuation (see [Appendix 2](#))
- Platelets < 75000/ μ L
- Pregnancy
- If a patient develops a medical condition that requires use of prohibited treatment as per [Section 5.5.8](#), or if patient exhibits a behavior of non-compliance regarding prohibited medications
- Patient received a live virus vaccination during the study
- If a patient experiences an unexpected hypersensitivity reaction of grade 4, as defined by the World Allergy Organization Grading System ([Cox 2010](#)), see [Appendix 3](#)
 - Lower or upper respiratory: Respiratory failure with or without loss of consciousness

- Or cardiovascular: Hypotension with or without loss of consciousness
- Emergency use of epinephrine due to anaphylactic or anaphylactoid reaction
- Any protocol deviation that results in a significant risk to the patient's safety

Patients who discontinue study treatment should NOT be considered withdrawn from the study. They will be expected to perform the Visit 313 (PSW) assessments four weeks after their last dose (except receiving study drug as a part of visit 313) and will be expected to perform all follow-up assessments (Visit 401-405). If they fail to return for these assessments for unknown reasons, every effort (e.g., telephone, e-mail, letter) should be made to contact them.

The investigator must provide follow-up medical care for all patients who are prematurely withdrawn from the study, or must refer them for appropriate ongoing care. This care may include initiating another treatment outside of the study as deemed appropriate by the investigator

The investigator must also contact the IRT to register the patient's discontinuation from study treatment.

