6.5.6 Pregnancy

Women of child-bearing potential only will have a urine pregnancy test at the visits specified in [Table 6-1](#). A positive urine pregnancy test requires a serum sample to be sent to the Central Lab and, during treatment epoch, immediate interruption of study medication until serum β -hCG is performed and found to be negative. If positive, the patient must be discontinued from the study drug but remain on the trial for the safety evaluation. Urine pregnancy test kits will be provided to the sites by the Central Lab.

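### Protocol 5.5.8 makes stopping a prohibited drug a condition of staying in the study, whereas 5.6.2 stops only QGE031 and keeps a patient who needs the drug in follow-up

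*Protocol*

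**What the plan says.** Protocol Section 5.5.8 prohibits the drugs in Table 5-1 once study treatment has started. If one was used, for any indication, "the patient must discontinue use of the prohibited treatment if he/she wishes to continue in the study". The next sentence, on live vaccines, uses a different term: "If the patient received a live virus vaccination during the study, the patient must discontinue study treatment".

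Protocol Section 5.6.2 lists the circumstances in which study treatment must stop. One of them reads "If a patient develops a medical condition that requires use of prohibited treatment as per" Section 5.5.8; the same bullet adds non-compliance with the rules on prohibited medication. The section then states: "Patients who discontinue study treatment should NOT be considered withdrawn from the study". These patients are to have the Visit 313 (PSW) assessments four weeks after their last dose and then Visits 401 to 405.

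The glossary separates stopping treatment from leaving the study: the first may or may not coincide with the second. Section 6.5.6 applies that distinction to a confirmed pregnancy: "the patient must be discontinued from the study drug but remain on the trial for the safety evaluation".

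**The concern.** The two sections attach different consequences to the same event. Section 5.5.8 ties staying in the study to stopping the prohibited drug. Section 5.6.2 ties only QGE031 to it. If the drug can be stopped, the sections can be reconciled. If the patient has a lasting need for it, they cannot be reconciled as worded: 5.5.8 makes continued participation conditional on stopping a drug that the patient needs, and 5.6.2 keeps the patient in without that condition. Long-term methotrexate and a beta-blocker for a new cardiac condition are plausible examples from Table 5-1.

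A site that worked from 5.5.8 alone could press the patient to stop a needed drug, or could end that patient's follow-up. This is a long-term safety study, and Section 3.2 gives safety after treatment discontinuation as a purpose of the follow-up epoch. The data at risk are scheduled laboratory tests and vital signs, new non-serious events, and serious events that the investigator does not suspect to be related to treatment.

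**Working it through.** **Text comparison, lasting medical need during the treatment epoch**

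| Question | 5.5.8 | 5.6.2 |
|---|---|---|
| Which use is covered? | Any indication | A condition that requires a drug prohibited under 5.5.8 |
| What must stop? | The prohibited drug | QGE031 |
| Does the patient stay in the study? | Only if the drug is stopped | Yes, stated explicitly |
| Are Visits 401 to 405 expected? | Not stated | Yes |

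Section 5.6.2 cites 5.5.8 by number, so both rules apply to the same patient.

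Could the 5.5.8 phrase simply mean staying on study treatment? That is probably the intent. But the glossary keeps the two ideas apart, and the neighbouring live-vaccine sentence uses the treatment term. The same paragraph also speaks of randomizing a patient, although Section 5.3 says there is no randomization. That suggests text carried over from another protocol.

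**What one patient would lose if a site applied 5.5.8 alone**

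The plan gives no figure to reproduce. Inputs:

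- Last scheduled dose on Day 337, Visit 401 on Day 365 and Visit 405 on Day 701 (Table 6-1).
- Patients who withdraw early are contacted every 4 weeks until 12 weeks after withdrawal (Protocol Section 6).
- The window for treatment-emergent adverse events ends 16 weeks after the last dose (SAP 2.5.1).
- Assumption: participation ends *w* weeks after the last dose, with *w* from 0 to 4.
- Assumption: Visits 401 to 405 are spaced from the last dose as for completers. Section 5.6.2 gives no date for Visit 401 in these patients.

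Results, in weeks after the last dose:

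- End of follow-up under 5.6.2: (701 − 337) / 7 = 364 / 7 = 52.
- End of scheduled contact after withdrawal: *w* + 12 = 12 to 16.
- Scheduled follow-up lost: 52 − (*w* + 12) = 40 − *w* = 40 to 36 weeks.
- Part inside the treatment-emergent window: 16 − (*w* + 12) = 4 − *w* = 4 to 0 weeks.
- Part after that window: 52 − 16 = 36 weeks.

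If Visits 401 to 405 instead keep their calendar weeks after an early stop, follow-up under 5.6.2 runs longer and so does the gap.

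**The case against.** The strongest reply is that the protocol already settles the case. Section 5.6.2 is specific, refers back to 5.5.8, and also covers the patient who will not comply. An ordinary reader would take 5.5.8 for drugs that can be stopped and 5.6.2 for the rest. Section 5.5.8 states a condition; it does not instruct anyone to withdraw a patient. Sections 5.6.3 to 5.6.5, on consent withdrawal, loss to follow-up and early termination, do not name prohibited medication either. Section 5.5.8 also tells sites to ask the sponsor when in doubt. All of this stands, and it is why the point is minor. It does not make the 5.5.8 sentence correct as written.

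A reader might infer that the protocol orders withdrawal, or that safety information would cease altogether. Neither is supported. No section orders withdrawal for prohibited medication. Adverse events already detected are followed until they resolve or are judged permanent (Section 7.1), and serious events suspected to be treatment-related stay reportable (Section 7.2.2).

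A reader might also infer the same contradiction for a patient who relapses in the follow-up epoch and starts a Table 5-1 drug, because 5.5.8 gives no end date for the ban. Section 3.1 says "the investigator should be contacted for an ad-hoc visit to consider treatment with standard of care or other therapy", and Section 5.6.1 says of relapsers that "they will be allowed to exit the study if desired and receive conventional therapy at the discretion of the investigator". But 5.6.1 can be read as exit first and treatment afterwards, and neither section says that a relapser may start a Table 5-1 drug and remain. That is an ambiguity, not a contradiction. Nor are the 17 patients in SAP 2.6.10 who took omalizumab after treatment examples of it, because omalizumab is not in Table 5-1.

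**Conclusion.** The mismatch is real and minor. It is confined to the literal wording of 5.5.8 against 5.6.2, for a patient with a lasting need for a Table 5-1 drug during the treatment epoch. A course that has ended, incidental use that is stopped, and live vaccination do not raise it.

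The number of patients affected cannot be derived from the documents. The loss of 36 to 40 weeks of scheduled follow-up per patient is conditional: it requires a site to apply 5.5.8 without 5.6.2, to end participation within 4 weeks of the last dose, and follow-up visits to be spaced as for completers. At most 4 of those weeks fall inside the treatment-emergent window. No hypothesis test is affected, because none is planned (Protocol 9.4.2).

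**What to change.** In Protocol 5.5.8:

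1. Replace *continue in the study* with *continue study treatment*.
2. Add that Section 5.6.2 governs any medically required use of a Table 5-1 drug, so that QGE031 is discontinued. Without this, the first change could suggest that a patient who needed the drug and then stopped it may go back to QGE031. Section 5.6.2 makes no such exception.
3. Add that use of a Table 5-1 drug is not by itself a reason for study withdrawal and that Visits 401 to 405 continue. The pregnancy wording in 6.5.6 is a suitable model.

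The cost is a changed phrase and two short statements, which can go into the next written amendment (Section 11.1 requires one). No visits are added, since 5.6.2 already expects them. No data field is added, since 5.5.7 already has all medications recorded. The SAP needs no change: its Section 2.5.6 already reports all available safety data. The one small downside is that some follow-up data will be collected while the patient is on other therapy.
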